## **Research Strategy**

### Screening:

Patients will be identified by the primary investigator ([name]) or one of the members of the VA team ([name], [name], [name]) during routine clinic appointments. Parents of infants with the diagnosis of infantile hemangiomas will be invited to enroll in the study prospectively. They will be given all the information regarding the study and the consent forms in clinic. All patients, including those who consent to the protocol or refuse, will follow the same protocol for therapy, but information will only be abstracted on those patients enrolled in the study.

### Blinding:

This is an open label study so patients and providers will not be blinded.

### Randomization:

Following enrollment and informed consent, patients will be randomized using a computer-generated randomization using permuted blocks of 6 patients. Randomization is to occur in the clinic at the time of the first prescription.

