**Sample Size:**

A sample size calculation was performed using best estimates in the literature provided by Theiler et al. (Theiler et al., 2021). Primary outcome was defined as number of awakenings per

night of sleep at 6 months of time on propranolol. In the Theiler et al study, patients on propranolol had 0.26 +/- 0.09 vs control patients of 0.21 +/- 0.1 awakenings per night. Utilizing a two-tailed analysis, we anticipate enrollment of 58 patients per treatment arm, giving our study 80% power with alpha 0.05. Given our number of annual patients (approximately 60 per year), we anticipate this study to be performed in 3 years. A concurrent Bayesian analysis will be performed.

We will analyze the data as two separate studies, each using the control (timolol) group as the reference. The BID propranolol group will be compared to the control group, as well as the TID group compared to control. This will allow us to see the effective change of sleep awakenings in each dosage group compared to control.

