### Prescription:

1. Control group: Patients with a small (<2cm) isolated infantile hemangioma are prescribed timolol 0.5% ophthalmic drops, a topical beta-blocker. Topical timolol has not demonstrated any concerns for sleep disturbances. Therefore, these patients will be enrolled as control patients in a non-randomized fashion.

Dosage for timolol 0.5% is 1 drop BID directly onto the hemangioma

2. Study groups: Patients with larger (>2cm) or multiple (>1) hemangiomas will be randomized to BID or TID dosage of propranolol. The prescription will be sent electronically to the pharmacy in the standard fashion for the practice. All patients will be initiated with the following schedule with medication administration to follow feeding:

Week 1: 0.5 mg/kg/day divided BID or TID

Week 2: 1 mg/kg/day divided BID or TID

Week 3: 2 mg/kg/day divided BID or TID. Patients will stay on this dosage until their 3 month follow up visit.

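### A fixed block size of 6, with open-label treatment and no described allocation concealment, lets an observer who sees the whole list know up to a quarter of BID/TID assignments in advance

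*Combined protocol and SAP*

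**What the plan says.** All sections cited are in the combined protocol and SAP.

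- **Method.** Under Randomization, after enrolment and consent, "patients will be randomized using a computer-generated randomization using permuted blocks of 6 patients". One block size is given, with no mention of varying it.
- **Place and time.** In the same section: "Randomization is to occur in the clinic at the time of the first prescription". Who carries out the randomisation is not stated.
- **Masking.** Under Blinding: "This is an open label study so patients and providers will not be blinded".
- **What is randomised.** Under Prescription, infants with larger or multiple "hemangiomas will be randomized to BID or TID dosage of propranolol". For timolol, "these patients will be enrolled as control patients in a non-randomized fashion".
- **Who recruits.** Under Screening, the investigator or another member of the vascular anomalies team identifies patients "during routine clinic appointments".
- **Size.** Under Sample Size: "we anticipate enrollment of 58 patients per treatment arm".
- **Sites.** The front page names two clinics. The plan does not say whether they share one list or have one each.

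No section says who holds the list, whether allocation is central, or whether clinic staff are kept unaware of the block size.

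**The concern.** In a block of known size, once one arm's quota is used up, the rest of the block is fixed. Computer generation makes the order random but does not hide it from someone who can count past assignments, and open-label treatment makes that counting possible.

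BID versus TID is the question posed under Research Question and PICO, and it is the only contrast that randomisation protects. The outcome is parent-reported sleep. The Background says that the clinic's practice is to move infants to TID when parents raise sleep concerns, and that this appears to help. Staff may therefore hold a view about which infants suit TID. If they can foresee the next arm, the choice of whom to invite, and when, could depend on it. The two propranolol groups could then differ at baseline in the characteristic being measured.

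**Working it through.** **Inputs.** Block size 6 (Randomization). Two randomised arms (Prescription). 58 per arm, so 2 × 58 = 116 randomised (Sample Size). A 3:3 split within blocks is inferred from the equal arms; it is not stated.

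**The plan's own figure.** The plan gives no predictability figure. Its sample size reproduces:
- Pooled SD = √((0.09² + 0.10²)/2) = 0.0951; planned difference = 0.26 − 0.21 = 0.05.
- n = 2 × (0.0951 × (1.960 + 0.842)/0.05)² = 56.8 per arm by the normal approximation, and 57.8 by the t-test, hence 58.
- Block size plays no part in this calculation.

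**Assignments known with certainty.** There are 20 equally likely orders of a 3:3 block.
- Position 4 is fixed if the first three match: 2/20 = 1/10.
- Position 5 is fixed if the first four hold three of one arm: 8/20 = 2/5.
- Position 6 is always fixed.
- Total: 0.1 + 0.4 + 1 = 1.5 of 6, or 25%.

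One list of 116 is 19 full blocks plus 2 infants: 19 × 1.5 = 28.5 (24.6%). With one list per clinic, assuming 58 infants each (9 full blocks plus 4), the figure is 2 × (9 × 1.5 + 0.1) = 27.2 (23.4%).

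**Partial sight of a shared list.** Suppose the observer knows where blocks start but sees each earlier assignment independently with probability v (assumed). An assignment is known only if all three members of the exhausted arm were seen, so the share is 0.25 × v³.

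| v | Share known with certainty |
|---|---|
| 1 | 25% |
| 0.75 | 0.25 × 0.422 = 10.5% |
| 0.50 | 0.25 × 0.125 = 3.1% |

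Simulation gave about 10-11% and 3%.

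**Best guess.** The best guess is always the arm that is behind so far. The chance of being right at positions 1 to 6 is 0.5, 0.6, 0.6, 0.7, 0.7 and 1, in total 4.1 of 6, or 68.3% (68.1% over 116).

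**Blocks of 4, 6 and 8 in random order.**
- *Certainty.* For an observer who sees every assignment and knows the set of sizes but not the current one, simulation of 3,000 lists of 116 gives 2.3% (0.023 × 116 ≈ 3 infants). If the current size were known, the share would be (1.333 + 1.5 + 1.6)/18 = 24.6%. Keeping the sizes from staff is therefore what removes certainty.
- *Guessing.* The arm that is behind has more places left whatever the block size, so the guessing rule needs no knowledge of size. Correct guesses per block are 2.833, 4.1 and 5.329, giving 12.262/18 = 68.1%. Simulation gave about 68%.

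**Illustration of possible bias.** Suppose steered infants differ from average by d in expected awakenings, in opposite directions for the two arms. The bias in BID minus TID is 2d × (share steered correctly − share steered wrongly).
- Acting only on certain assignments: 2 × 0.25 × d = 0.5d now, and 2 × 0.023 × d ≈ 0.05d with varied blocks.
- Acting on every guess: 2 × (2 × 0.683 − 1) × d = 0.73d now, and 2 × (2 × 0.681 − 1) × d = 0.72d with varied blocks.

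The value of d is unknown. For an assumed d of 0.1 to 0.3 SD, 0.5d is 0.005 to 0.014 awakenings. That is 10% to 29% of 0.05, which is a propranolol-control difference and serves here only as a scale. These figures assume that every opportunity is noticed and used.

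**The case against.** The strongest case against has four parts.

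1. **The 25% needs an observer who sees everything.** The plan has two clinics and several recruiters. Open label means that patients and providers know the treatment given; it does not mean that each clinician sees every assignment. This stands, so 25% is a ceiling.

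2. **There is little room to act.** Randomisation follows consent. The plan expects about 60 patients a year in all; if a third are timolol controls, about 40 a year are randomised, fewer than one a week. There is rarely a queue to reorder, and waiting for a preferred arm would often mean delaying a first prescription. This limits the mechanism but does not remove it, because the decision to invite a family comes before consent.

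3. **The planned primary comparisons lie elsewhere.** Primary Outcome and Sample Size compare each propranolol arm with timolol, which is assigned by lesion size and number. That non-randomised reference group is a larger, separate problem. The Hypothesis nevertheless contrasts the two comparisons, so steering between BID and TID would affect it as well.

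4. **Varying the blocks does not stop guessing.** This is correct.

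A reader might also infer that the block size was public during accrual, or that the prescribers themselves randomise. The documents support neither: the size is stated in the protocol, and the Randomization section gives only place and time.

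**Conclusion.** The point holds as a design weakness that is cheap to correct. One fixed block size, open-label treatment and no described concealment leave up to 25% of BID/TID assignments (about 28 of 116) knowable in advance. This rests on 3:3 blocks and on an observer who sees every earlier assignment on a list. Under the assumed partial sight of a shared list, the share is about 10-11% or 3%.

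Three stronger readings are not supported:
- *That a quarter of assignments will in fact be known.* The documents do not show who sees the list or how it is organised.
- *That selection bias has occurred.* The documents show an opportunity and a plausible motive, not an event.
- *That undisclosed sizes would make the next arm unguessable.* Accuracy stays near 68% because guessing uses only the running count.

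The sample size is unaffected.

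**What to change.** In the Randomization section, replace the fixed block of 6 with wording such as: *Infants eligible for propranolol will be allocated 1:1 to BID or TID in permuted blocks whose size varies at random. Block sizes will be recorded in a document not available to clinic staff. The list will be held in the study database, and each assignment will be revealed only after consent and eligibility have been recorded.* Blocks of 4, 6 and 8 would serve, without being named in the protocol. State also whether the two clinics share a list or have one each, and who prepares it.

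Concealing the list until consent and eligibility are recorded matters as much as varying the blocks. It prevents staff from reading the next assignment, although guessing from past assignments remains possible.

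The cost is a sentence or two and a regenerated list for infants not yet randomised. The Confidentiality section already plans a REDCap database, which could hold the list. If accrual stops within a block, the arms could differ by up to 4 infants per list (half of a block of 8) instead of up to 3 now (half of 6), which has little effect with 58 per arm.

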**NCT05479123**

**Version Date: 06/02/2022**

**Protocol Title:** Assessing the Impact of Dosage Frequency of Propranolol on Sleep Patterns in Patients with Infantile Hemangiomas.

**Principal Investigator:** [name]

**Co-Investigators:** [name], [name], [name], [name], [name], [name]

**Sample Size:** 174

**Number of Sites:** Two study sites – Pediatric Plastic Surgery Clinic at the University of Texas Health Sciences Center at Houston and Dermatology Clinic at the University of Texas Health Sciences Center at Houston

**Study Duration:** Three years

**Subject Duration:** Up to age 18 months

**Version:** 1.4

**Most Recent Revision** 2/7/2022

---

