**Study Population:**

Inclusion Criteria:

1. Patients with clinically diagnosed hemangiomas.
2. Age <18 months
3. English or Spanish speaking only

Exclusion Criteria:

1. Parents who do not consent to the study.
2. Significant cardiac or pulmonary disease who are unable to tolerate oral propranolol
3. Age >18 months
4. Non-English or Spanish speaking parents.

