**Study Design:**

Prospective, single center, randomized controlled trial – parallel groups

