**Primary Outcome:**

1. Using the BISQ, number of sleep awakenings per night between the control (timolol) group and the BID propranolol group at 6 months on therapy.
2. . Using the BISQ, number of sleep awakenings per night between the control (timolol)group and the TID propranolol group at 6 months on therapy.

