### Sleep Survey:

In this study, we propose to use the Brief Infant Sleep Questionnaire (BISQ) to record and quantify caregiver reports of infant sleep. The BISQ has been validated as a multi-dimensional survey for evaluating infant sleep due to its reliability and high specificity of sleep parameters (Sadeh, 2004; Del-Ponte et al., 2020). Parents will be offered this study at each of the clinic visits (every 3 months) from the date of initial prescription until termination of the medication (18 months of age). Patients in all three groups (Timolol, BID Propranolol, and TID Propranolol) will be given this survey.

Follow up: Once a prescription is initiated, all patients with infantile hemangiomas stay on the medication until 18 months of age. Patients are seen every three months, either in person or virtual visits. During that visit, a recent weight is used to adjust their dosage of the oral propranolol to the new appropriate level. Each of these visits will be an opportunity for the sleep survey to be given.

Study Termination: After 18 months of age, all patients are removed from medication (timolol and propranolol). After this visit and final sleep assessment, all patients will be removed from the study.

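### Age and clinic are handled in neither the BID/TID randomisation nor the analysis; the cost is precision, not bias, and covariate adjustment recovers most of it

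*Combined protocol and SAP*

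**What the plan says.** The Randomization section gives the whole allocation method: patients are "randomized using a computer-generated randomization using permuted blocks of 6 patients", in clinic, when the first prescription is written. It names no stratification factor, and no other section does. It also gives no allocation ratio; 1:1 is inferred here from the equal planned arm sizes.

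The Prescription section shows what is randomised: "Patients with larger (>2cm) or multiple (>1) hemangiomas will be randomized to BID or TID dosage of propranolol". The timolol infants are not: "these patients will be enrolled as control patients in a non-randomized fashion". BID versus TID is therefore the only randomised contrast.

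The title page lists "Two study sites", a plastic surgery and a dermatology clinic of one university. Study Design reads "Prospective, single center, randomized controlled trial". Neither place, nor the Randomization section, says whether the clinics share one sequence.

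On age, the inclusion criterion is "Age <18 months", with no lower limit. Under Sleep Survey, "all patients with infantile hemangiomas stay on the medication until 18 months of age". The first primary outcome is the "number of sleep awakenings per night between the control (timolol) group and the BID propranolol group at 6 months on therapy"; the second is the same for TID.

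The Sample Size section holds the only analysis text. It sets out two separate comparisons with timolol and mentions no covariate. It contains no direct TID versus BID comparison, although that is what the Research Question and the PICO statement ask.

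**The concern.** Age at first prescription and clinic are both known at randomisation, and date of birth is already listed under Data Collection. A trial can deal with such factors by stratifying, by adjusting, or both. As written, this plan does neither.

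Unstratified blocks balance the total numbers on BID and TID. They do not balance the arms on starting age or within a clinic. A night-waking outcome assessed across a wide span of infancy could plausibly vary with age, so age may add avoidable noise to the comparison that answers the research question. A visible imbalance in starting age would also invite doubt about the result, with no prespecified analysis to answer it.

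**Working it through.** **Inputs from the documents.** Sample Size: means 0.26 and 0.21 awakenings per night, SDs 0.09 and 0.10, 58 per arm, 80% power, two-sided alpha 0.05. Two randomised arms give 2 × 58 = 116 infants.

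**Assumptions not in the documents.** 1:1 allocation; a correlation r between age and awakenings of 0.3 to 0.5; a factor present in 50% of infants (age group) or other shares (clinic).

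**1. The plan's own figure.** Pooled SD = √((0.09² + 0.10²)/2) = 0.0951. For a difference of 0.05, the normal approximation gives 57 per arm and the t-test 57.8, rounded up to 58. Power at 58 per arm is 80.8% (normal) or 80.1% (t). The stated size reproduces.

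**2. Starting ages that count.** Treatment stops at 18 months of age and the endpoint is at 6 months on therapy. A contributing infant must start by about 18 − 6 = 12 months. The relevant range is about 0 to 12 months, not 0 to 18.

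**3. How often imbalance occurs.** In simulations of 116 infants in unstratified blocks of 6:
- factor present in 50%: the arms differ by at least 10 points in about 31% of trials, and by at least 15 points in about 11–12%;
- factor present in 30%: about 25% and 7–8%.

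For continuous age, the standardised difference has SE √(2/58) = 0.186, so its 95% limits are ±1.96 × 0.186 = ±0.36. It exceeds 0.2 in absolute value in 28% of trials and 0.3 in 11%.

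**4. What an imbalance does to TID minus BID.** For a 50:50 factor with correlation r, the difference between its two levels is 2 × r × SD. A 10-point imbalance shifts the contrast by 0.10 × 2 × r × 0.0951:
- r = 0.3: 0.10 × 0.057 = 0.006;
- r = 0.5: 0.10 × 0.095 = 0.010.

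For continuous age at its 95% limit, the shift is r × 0.364 × 0.0951:
- r = 0.3: 0.010;
- r = 0.5: 0.017.

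For scale, the unadjusted standard error of the contrast is 0.0951 × √(2/58) = 0.0177.

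**5. An upper bound.** A 50:50 factor worth d awakenings contributes variance d²/4, which cannot exceed 0.0951² = 0.00905. So d cannot exceed 2 × 0.0951 = 0.19, and reaches that only if the factor explains all variation within arms.

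**6. Type I error.** In 3,000 simulated trials at each value of r, with no treatment effect, the unadjusted test rejected in 4.8% for both.

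**7. Gain from adjustment.** Adjusting for age reduces the SD to 0.0951 × √(1 − r²). Power at 58 per arm for a 0.05 difference (normal approximation), against 80.8% unadjusted:
- r = 0.3: 84.3%;
- r = 0.5: 90.5%.

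Simulated power agrees: 80.0% unadjusted and 83.9% adjusted at r = 0.3; 79.1% and 89.0% at r = 0.5.

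**The case against.** The strongest reply is that chance imbalance under valid randomisation is not a flaw. It is already in the standard error, type I error holds near 5%, and adjustment would recover most of the lost precision with no change to the list. That stands, which is why the fix puts adjustment first. It does not excuse the plan's silence, because no adjustment is specified.

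A reader might infer more than the documents support:

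- That imbalance could create or hide the planned effect. A factor worth 0.2 awakenings would give a 0.02 shift at a 10-point imbalance, or 40% of 0.05. But 0.2 exceeds the 0.19 ceiling in step 5. Moreover, 0.05 is the propranolol–control difference; the plan states no TID–BID difference, so 0.05 is only a scale reference.
- That age and clinic are main drivers of infant sleep. No section says so. An age effect is plausible, but its size here is assumed. Clinic is at most a reasonable design factor; nothing shows that the two clinics differ in staff or referral mix.
- That the single-center label is an error. Two clinics of one university can fairly be called one center. What is missing is whether they share a sequence.

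Stratifying also has a drawback. The Blinding section makes the trial open label and the block size is stated, so separate sequences of fixed size would make the next allocation easier to predict.

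**Conclusion.** The point holds as a modest improvement to design and analysis. Age and clinic are dealt with in neither the described randomisation nor the described analysis of the only randomised contrast. The plan is silent on stratification; it does not rule it out.

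The consequence is lost precision and some loss of credibility, not bias or an inflated alpha. An imbalance of 10 points in a half-and-half factor is common, but the resulting shift is below one standard error of the contrast, even for age at its 95% limit with r = 0.5 (0.017 against 0.0177). Both the size of the shift and the gain in power depend on the assumed correlation of 0.3 to 0.5; with a weaker correlation, both shrink.

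The larger weakness lies elsewhere: both primary comparisons use a non-randomised control, and neither stratifying BID/TID nor adjusting for these two covariates repairs that.

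**What to change.** 1. In the Sample Size section's analysis text, add a direct TID versus BID comparison of awakenings at 6 months on therapy, adjusted for age at first prescription (continuous) and clinic. Adjust the two timolol comparisons for the same covariates. The power gain in step 7 applies to the randomised contrast; against timolol it will be smaller if starting age differs between the groups.
2. If the list can still be regenerated, stratify BID/TID 1:1 by age at first prescription (under 6 months versus 6 months or more) and by clinic, giving four strata, with concealed and randomly varying block sizes. State the ratio and the strata in the Randomization section.
3. Whether or not the list changes, make the title page, Study Design and Randomization sections say consistently whether the two clinics share one sequence.

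The cost of item 1 is a few lines of analysis text; age follows from date of birth, clinic must be recorded, and the planned 58 per arm is unchanged. Item 2 needs a new list and leaves up to four incomplete blocks at close. Each can unbalance its stratum by at most half a block (3 infants for a block of 6), so final arm sizes may differ by a few infants. If the block size stays fixed and known, allocation becomes slightly more predictable. If the list cannot be changed, item 1 alone recovers most of the benefit.

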### Prescription:

1. Control group: Patients with a small (<2cm) isolated infantile hemangioma are prescribed timolol 0.5% ophthalmic drops, a topical beta-blocker. Topical timolol has not demonstrated any concerns for sleep disturbances. Therefore, these patients will be enrolled as control patients in a non-randomized fashion.

Dosage for timolol 0.5% is 1 drop BID directly onto the hemangioma

2. Study groups: Patients with larger (>2cm) or multiple (>1) hemangiomas will be randomized to BID or TID dosage of propranolol. The prescription will be sent electronically to the pharmacy in the standard fashion for the practice. All patients will be initiated with the following schedule with medication administration to follow feeding:

Week 1: 0.5 mg/kg/day divided BID or TID

Week 2: 1 mg/kg/day divided BID or TID

Week 3: 2 mg/kg/day divided BID or TID. Patients will stay on this dosage until their 3 month follow up visit.

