**Hypothesis:**

We anticipate that patients receiving the TID dosing regimen of oral propranolol will demonstrate fewer sleep awakenings compared to the control group than the BID dosing regimen compared to the control.

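### Both primary contrasts are non-randomised because lesion size and number decide who receives timolol, yet the plan states no control of confounding; adjustment for first-visit awakenings and age should be prespecified.

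*Combined protocol and SAP*

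**What the plan says.** Under Prescription, an infant with a single lesion under 2 cm is given topical timolol: "Therefore, these patients will be enrolled as control patients in a non-randomized fashion". Randomisation applies only to the others: "Patients with larger (>2cm) or multiple (>1) hemangiomas will be randomized to BID or TID dosage of propranolol". Study Design labels the whole study as "Prospective, single center, randomized controlled trial".

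The first primary outcome is the "number of sleep awakenings per night between the control (timolol) group and the BID propranolol group at 6 months on therapy"; the second is the same comparison for TID. The Sample Size section adds: "We will analyze the data as two separate studies, each using the control (timolol) group as the reference". It bases 58 per arm on published values of "0.26 +/- 0.09 vs control patients of 0.21 +/- 0.1 awakenings per night", with 80% power and two-sided alpha 0.05.

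No section names an analysis model, covariate, matching, stratification or weighting. A concurrent Bayesian analysis is announced but not described.

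The data needed for adjustment are largely planned. The Sleep Survey section offers the BISQ from the date of the initial prescription and every 3 months afterwards. Under Randomization, "Randomization is to occur in the clinic at the time of the first prescription". Data Collection records date of birth. A first-visit BISQ would ordinarily precede the first dose, but no section says so or names it as a baseline.

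**The concern.** Lesion size and number, not chance, separate timolol from propranolol infants, so neither primary contrast has the protection of randomisation. Entry is open to any age under 18 months and treatment ends at 18 months of age. An infant assessed at 6 months on therapy may therefore be anywhere from about 6 to 18 months old. Nothing in the plan balances age or baseline sleep between timolol and propranolol.

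Timolol is the shared reference, so an imbalance on that side shifts both primary results in the same direction. Two agreeing results would then not corroborate each other. A false drug effect could appear, or a real one could be hidden.

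Prespecification matters more than usual because the study is open label and sleep is reported by caregivers. Adjustment chosen after the results are seen would be open to selection.

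**Working it through.** **1. The plan's own figure.** Inputs from Sample Size: means 0.26 and 0.21, SDs 0.09 and 0.10, 58 per arm, two-sided 0.05.

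- Pooled SD = sqrt((0.09² + 0.10²)/2) = 0.0951.
- Standardised difference = 0.05/0.0951 = 0.526.
- Standard error in SD units = sqrt(2/58) = 0.1857.
- Power of an unadjusted t-test (114 df) = 0.801. Solving for 80% gives 57.8, so 58 per arm.

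The stated size is reproduced, with no allowance for adjustment or confounding.

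**2. Effect of a baseline gap.** The documents give no gap or correlation, so both are assumed. With no drug effect, a gap of g SD in baseline awakenings and a baseline-to-6-month correlation r shift the unadjusted contrast by r × g SD. The noncentrality is r × g/0.1857. For r = 0.5 and g = 0.4 it is 0.20/0.1857 = 1.08.

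| r | Gap (SD) | Shift (SD) | False-positive rate | Power if the gap opposes the planned effect |
|---|---|---|---|---|
| 0.3 | 0.2 | 0.06 | 6.2% | 70% |
| 0.3 | 0.4 | 0.12 | 9.8% | 58% |
| 0.5 | 0.2 | 0.10 | 8.3% | 62% |
| 0.5 | 0.4 | 0.20 | 18.7% | 41% |

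The false-positive column is in SD units and does not depend on the plan's SD. The power column does, through 0.526. A gap in age would act in the same way, with its own correlation.

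**3. What adjustment removes.** In a simulation of 8,000 trials per case (r = 0.5, gaps 0.2 and 0.4), rejection under the null was 8.7% and 18.9% unadjusted, and 4.3% and 5.1% adjusted. That assumes baseline is measured without error. If its reliability were 0.6, then 1 − 0.6 = 40% of the baseline-carried shift would remain.

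**4. Power after adjustment.** Variance in SD² units = (1 − R²) × (2/n + D²/(2(n − 1))), with 112 df at n = 58. R² is the share of outcome variance explained, and D is the joint distance between groups on the two covariates. Example with R² = 0.09, D² = 0.64: 0.91 × (0.03448 + 0.64/114) = 0.0365; noncentrality 0.526/sqrt(0.0365) = 2.75; power 78%.

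| R² | D = 0 | D = 0.4 | D = 0.8 | Both covariates 0.8, uncorrelated (D² = 1.28) |
|---|---|---|---|---|
| 0.25 | 90% | 89% | 85% | 80% |
| 0.09 | 84% | 82% | 78% | 72% |
| 0.01 | 81% | 79% | 74% | 69% |

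For R² of 0.09 and 0.01, restoring 80% by this formula takes 62 and 67 per arm at D = 0.8, or 70 and 76 at D² = 1.28.

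**5. Dependence on the plan's SD.** All power figures take 0.05 and 0.0951 as given. If awakenings were whole-number reports (an assumption), the smallest possible SDs would be sqrt(0.21 × 0.79) = 0.407 and sqrt(0.26 × 0.74) = 0.439, pooled 0.423. Power at 58 per arm would then be about 10%, adjusted or not.

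**The case against.** The protocol does not hide the non-random enrolment; Prescription states it, and the randomised label is accurate for BID versus TID. The gap, correlation and reliability used above are all assumed. Lesion size and number define the groups, so they do not overlap and cannot be adjusted for, and open-label caregiver reporting is also untouched. Regression on baseline is one of several defensible choices, alongside change scores, propensity weighting or a count model.

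The Hypothesis expects TID to show "fewer sleep awakenings compared to the control group than the BID dosing regimen compared to the control". Any imbalance on the timolol side cancels in that difference of differences, which reduces to TID versus BID.

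Most of this stands, and it limits the point. No particular model can be called the only right one, and adjustment reduces confounding without removing it. But disclosing how infants are enrolled does not supply an analysis that allows for it. The cancellation helps only the TID-versus-BID comparison, which Research Question and PICO ask about but Primary Outcome does not list. It does not protect either primary outcome taken alone.

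A reader might infer that the timolol comparisons are shown to be biased. The documents do not support that, because they report no imbalance. Nor do they support dismissing the whole trial as non-randomised.

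**Conclusion.** The concern holds as a gap in the analysis plan that should be closed. Neither primary contrast is randomised, no control of confounding is stated, and the sample size assumes an unadjusted, unconfounded comparison. The illustrative size is a false-positive rate of about 6% to 19% instead of 5%, for baseline gaps of 0.2 to 0.4 SD and correlations of 0.3 to 0.5. Those inputs are hypothetical, so confidence in the practical size is moderate; the design facts are plain in the text.

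It might also be inferred that adjustment would make the timolol contrasts equivalent to randomised ones, or that it guarantees 80% power at 58 per arm. Neither follows. Lesion size and number remain confounded with treatment, a single parent-reported baseline carries error, and power falls below 80% in some of the cases shown.

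**What to change.** 1. Prespecify that each 6-month timolol contrast is adjusted for first-visit BISQ awakenings and age at the 6-month assessment. Linear regression with robust standard errors would serve, with a count model as a sensitivity check.
2. State that the first BISQ is completed at the prescription visit before the first dose.
3. In Study Design, Primary Outcome and Sample Size, describe both timolol contrasts as non-randomised. State the residual confounding from lesion size and number, which cannot be adjusted for, and from error in a parent-reported baseline.
4. Report TID versus BID from the same data as the only randomised contrast and the one that Research Question and PICO ask about.
5. State that the 80% power applies to the unadjusted, unconfounded comparison under the SDs in Sample Size.

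**Cost.** A few sentences, and a pre-dose survey at a visit where it is already offered. Precision usually improves. Taking the plan's effect and SD as given, power at 58 per arm could fall to about 74% to 78% with a joint covariate gap of 0.8 SD and weak prediction (R² 0.01 to 0.09), or to about 69% to 72% if both uncorrelated covariates differ by 0.8 SD. With HC3 robust errors, simulation of the 0.8 SD joint-gap cases gave slightly less, 72% to 77%.
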